### 7.3. Protocol Deviations

Protocol deviations will be recorded and detailed in a data listing. Deviations will be identified as major or minor, as evaluated by the monitoring team.

### 7.4. Demographic and Baseline Characteristics

Subject demographics using the ITT set will be summarized, and repeated on the BSS. These will include age, sex (Male / Female), child-bearing potential (Yes / No), ethnicity (Hispanic or Latino / Not Hispanic or Latino), race (American Indian or Alaska Native / Asian / Black or African American / Native Hawaiian or Pacific Islander / White / Other), years of education, country (United Kingdom/Belgium / Australia/New Zealand), baseline height (cm), baseline weight (kg), and BMI (kg/m^2). Data will be presented by study cohort, disease criteria, and sequence.

#### *Clinical and Cognitive Scales*

The Montreal Cognitive Assessment (MoCA, for all subjects) is a brief cognitive screening tool and includes measures of expressive and receptive language, memory, and praxis. There are items that screen executive functions and working memory. The scores range from 0 to 30 with scores lower than 26 suggesting cognitive disorder.

The Digital Symbol Substitution Test (DSST, for MCI subjects only) integrates complex neuropsychological processes and measures aspects of cognitive function, including cognitive and psychomotor speed, attention, visual scanning, and executive function. The maximum attainable score is 135, with higher scores indicating better performance. Further details of the test can be found in Section 5.3.6.1 of the study protocol.

The Modified Hoehn and Yahr Scale (MHYS, for RBD+PD, DLB, and PDD subjects only) is a clinician-completed rating scale that is used to describe the symptom progression of PD. It parses PD into 5 stages, with the additional of stages 1.5 and 2.5 to account for the intermediate course of PD. Details on staging can be found in Section 5.3.6.3 of the study protocol.

The REM Sleep Behavior Disorder Single-Question Screen (RBD1Q, for RBD+PD subjects only) is a single “yes-no” question as follows: “Have you ever been told, or suspected yourself, that you seem to ‘act out your dreams’ while asleep (for example, punching, flailing your arms in the air, making running movements, etc.)?”

MoCA and DSST, MHYS, and RBD1Q data will be summarized in the demographics and baseline characteristics tables and listed by subject.

Descriptions of the Hospital Anxiety and Depression Scale (HADS) can be found in section 8.2 below, and descriptions of Neuromelanin-MRIs can be found in section 8.3 below. Baseline HADS depression and anxiety subscores and neuromelanin MRI contrast-to-noise (by scanner type) will be summarized in the demographics and baseline characteristics table.

Sponsor: CuraSen Therapeutics, Inc.  
Protocol Number: CST103/CST107-CLIN-011  
Version and Date: [REDACTED] v1.0 / 24May2022

These demographic and baseline data will be listed. Additionally, drugs of abuse and alcohol findings and serology data will be listed.

### 7.5. Medical History

Medical history among the ITT set will be summarized and listed by Medical Dictionary for Regulatory Activities (MedDRA 23.1) system organ class (SOC) and preferred term (PT), and verbatim term as collected in the study database.

### 7.6. Prior and Concomitant Medication

The incidence of medication use will be summarized by WHO Drug Dictionary (B3, 2020-09-01) anatomic therapeutic chemical classification (ATC) Level 2 classification (i.e., therapeutic main group) and preferred name. A subject will be counted only once at each level of reporting. Prior medications are those which have been identified to have been discontinued prior to the treatment start date (e.g. taken exclusively during the pre-therapy period). Concomitant medications are those which have been identified to have been taken at any point after first dose. Concomitant medication use will be summarized on the ITT set and presented by study cohort, disease type, and sequence, as applicable.

All prior and concomitant medication data will be listed including the verbatim and preferred drug name and ATC Level 2. Procedures and non-med therapies will also be listed.

### 7.7. Study Drug Exposure and Compliance

Drug exposure will be summarized as a continuous variable in the Safety Set. The duration of drug exposure will be calculated as follows:

$$\text{Duration of Exposure (days)} = \text{Date of Last Dose} - \text{Date of First Dose} + 1$$

In addition, subjects will be assessed for compliance to drug dosing for CST-103 and CST-107 based on number of tablets/capsules dispensed and returned will be provided. The total number of tablets taken will be calculated as the sum of tablets dispensed minus the sum of tablets returned.

- 28 CST-103 or placebo capsules are expected to be taken during each treatment period, per protocol (i.e., two capsules once daily). Summaries will be presented by treatment (i.e., Placebo and CST-103/CST-107) based on each subjects' exposure to each treatment.
- 14 CST-107 or placebo capsules are expected to be taken during each treatment period, per protocol (i.e., one capsule once daily). Summarized will be presented by treatment (i.e., Placebo and CST-103/CST-107) based on each subjects' exposure to each treatment.

Sponsor: CuraSen Therapeutics, Inc.  
Protocol Number: CST103/CST107-CLIN-011  
Version and Date: [REDACTED] v1.0 / 24May2022

Drug exposure will be summarized by cohort, disease type, and treatment taken at time of data collection.

Study drug administration data, including date and time of doses, location of dosing, total number of tablets/capsules dispensed and returned, and compliance will be listed.

## 8. ENDPOINT ANALYSES

All inferential analyses are exploratory in nature given that this study was not powered based on any statistical assumptions. All efficacy data will be presented by cohort, disease type, and treatment assigned at the time of data collection.

### 8.1. Primary Endpoint and Analyses

#### Cohort A

Analyses of FERT data will be summarized in a separate analysis plan.

#### Cohort B

Due to the small sample size, all primary endpoint data for Cohort B subjects will be listed only using the FAS.

#### *Waking EEG*

Analyses of waking EEG data will be summarized in a separate analysis plan.

#### *Activity Tracking (AUS/NZ Subjects Only)*

The BioStamp nPoint device will be worn continuously for the 7 days prior to the Treatment Period 1 through the Day 1 visit (Baseline period), and re-dispensed at each of the Day 1 Visits in both periods, worn for 14 days, and removed on Day 14. During each of the three periods in which the subject wears the device, the device calculates 49 cumulative metrics for each day worn within the period. The metrics are then aggregated by study period (Baseline period, Treatment Period 1, Treatment Period 2). The 7 metrics related to activity tracking/classification are:

- Percent Wake Time defined as the percentage of sensor wear time spent awake. All time not spent awake is time spent asleep (identified in the raw data as `wake_percent`).
- Percent Moving Time defined as the percentage of waking time spent moving (sum of walking and other) (identified in the raw data as `moving_percent`).
- Percent Moving Other Time defined as the percentage of time spent moving but not walking (identified in the raw data as `moving_other_percent`).
- Percent Walking Time defined as the percentage of time spent walking

Sponsor: CuraSen Therapeutics, Inc.  
Protocol Number: CST103/CST107-CLIN-011  
Version and Date: [REDACTED] v1.0 / 24May2022

- Moving Activity Count defined as the activity counts per hour during moving periods (identified in the raw data as activity\_moving).
- Resting Activity Count defined as the activity counts per hour during resting periods
- Wake Activity Count defined as the activity counts per hour during moving and resting periods (identified in the raw data as activity\_resting).

All BioStamp aggregated data will be listed.

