1.5. Rationale for CST-107 Dose Selection

CST-107 is included in this study to attenuate the peripheral effects commonly caused by β_2 -AR agonists which include increased heart rate, palpitations, tremors, decreases in potassium and increases in blood glucose. Previous CuraSen studies exploring low doses of CST-107 co-administered with 80 μg of CST-103 suggest that a 1 mg dose can attenuate these peripheral effects. This is in marked contrast to the usual initial dose for hypertension which is 40 mg CST-107 tablets once daily. The usual maintenance dose is 40 or 80 mg administered once daily and doses up to 240 or 320 mg administered once daily may be needed.

In the treatment of reactive airways disease, the use of a β -AR blocker is not normally recommended along with CST-103 in that the therapeutic effect of the agonist can be antagonized and would risk triggering a severe bronchospasm in patients with asthma. Since this study does not include patients with reactive airways disease and CST-103 is not being used for its bronchodilatory properties, this contraindication is not applicable to this study.

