Heart Rate Variability (HRV) is computed for each activity period using two methods, LF/HF which is a ratio of low frequency to high frequency and RMSSD which is the root mean square of the successive differences. For each of the 8 metrics below, a set of descriptive statistics is computed (coefficient of variation, minimum, maximum, mean, 5th, 25th, 75th, 95th percentiles, standard deviation), and the mean of each parameter will be assessed using the mixed modeling described later on:

  - Sleeping HRV LF\_HF (identified in the raw data as hrv\_lfhf\_sleeping).
  - Sleeping HRV RMSSD (identified in the raw data as hrv\_rmssd\_sleeping).
  - Resting HRV LF\_HF (identified in the raw data as hrv\_lfhf\_resting).
  - Resting HRV RMSSD (identified in the raw data as hrv\_rmssd\_resting).
  - Moving HRV LF\_HF (identified in the raw data as hrv\_lfhf\_moving).
  - Moving HRV RMSSD (identified in the raw data as hrv\_rmssd\_moving).
  - Waking HRV LF\_HF (identified in the raw data as hrv\_lfhf\_wake).
  - Walking HRV RMSSD (identified in the raw data as hrv\_rmssd\_wake).
- Temporal pedometry:
  - Average Gait Cadence as defined as steps per minute during walking (identified in the raw data as avg\_gate\_cadence).
  - Step Count Rate as defined as step counts per hour during periods classified as walking (identified in the raw data as step\_count\_rate).

If a subject has at least 5 days of sensor wear within each period, the metrics will be aggregated for each period to obtain a single value. Descriptive statistics of the 17 metrics noted above, as well as the 7 activity metrics noted in Section 8.1 above, and change from baseline will be reported for both Cohort A and Cohort B subjects. A mixed model with change from baseline period as the dependent variable, baseline period value as a covariate, treatment sequence, post-baseline period (i.e., 1, 2), disease type, and treatment as fixed effects, and subject as a random effect will be analyzed for these posture, sleep, autonomic function, activity tracking, and temporal pedometry parameters for all subjects and LS means, LS mean differences, and p-values will be presented.

*Epworth Sleepiness Scale (ESS)*

Sponsor: CuraSen Therapeutics, Inc.  
Protocol Number: CST103/CST107-CLIN-011  
Version and Date: █████ v1.0 / 24May2022

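### SAP 8.1 names the resting-activity variable as the source for Wake Activity Count, so resting-only counts would be modelled under the wake label if programmed as written

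*SAP*

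**What the plan says.** SAP 8.1, Activity Tracking, lists seven BioStamp activity metrics, most with the raw-data name to be used. Three of them matter here:

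- "Moving Activity Count defined as the activity counts per hour during moving periods", with source `activity_moving`.
- "Resting Activity Count defined as the activity counts per hour during resting periods", with no source named.
- "Wake Activity Count defined as the activity counts per hour during moving and resting periods (identified in the raw data as" and then `activity_resting`.

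Percent Walking Time, in the same list, also has no source.

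For Cohort B as a primary measure, these data are only listed. SAP 8.2, BioStamp, takes them further: "Descriptive statistics of the 17 metrics noted above, as well as the 7 activity metrics noted in Section 8.1 above" are to be produced for both cohorts. A mixed model of change from the baseline period then gives least-squares means, differences and p-values. SAP 2.1 limits BioStamp to Australian and New Zealand subjects, and SAP 8.2 calls all inference exploratory.

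SAP 8.2 also contains a metric labelled "Walking HRV RMSSD (identified in the raw data as hrv\_rmssd\_wake".

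**The concern.** Raw-data names are put in a SAP to direct programming. Where the name and the definition disagree, a programmer who follows the name produces a different quantity from the one a reader of the table expects. Here the wake row would hold counts from resting periods alone. Resting Activity Count would then either have no data or repeat the same variable under a second name.

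Activity tracking is a named primary measure for Cohort B, and BioStamp activity is a secondary endpoint for both cohorts. A mislabelled row would therefore go into the study report with a treatment difference and a p-value attached. Nothing else in the protocol or SAP corrects the mapping.

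**Working it through.** **1. Is the mapping wrong on the SAP's own terms?** The four activity-count metrics, set side by side:

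| Metric | Periods in the definition | Source named |
|---|---|---|
| Moving Activity Count (8.1) | moving | `activity_moving` |
| Resting Activity Count (8.1) | resting | none |
| Wake Activity Count (8.1) | moving and resting | `activity_resting` |
| Sleeping Activity Counts (8.2) | sleeping | `activity_sleeping` |

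In the two rows that are complete and consistent, the suffix names the period. By that pattern `activity_resting` holds resting periods only, so it belongs in the second row and does not meet the definition in the third. The documents do not give the correct wake variable.

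**2. Does it reach an analysis?** Yes. SAP 8.2 brings in all seven activity metrics for description, and names activity tracking among the parameters to be modelled.

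**3. How large could the error be?** Let m be the share of waking time spent moving, and k the ratio of the moving count rate to the resting count rate. With the resting rate set to 1:

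- true wake rate W = m × k + (1 − m) × 1
- value printed under the wake label = 1
- printed ÷ true = 1 ÷ W

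The documents give neither m nor k. The ranges below are assumptions.

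| m | k = 5 | k = 10 | k = 20 |
|---|---|---|---|
| 0.1 | 0.71 | 0.53 | 0.34 |
| 0.2 | 0.56 | 0.36 | 0.21 |
| 0.3 | 0.45 | 0.27 | 0.15 |
| 0.5 | 0.33 | 0.18 | 0.10 |

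The two extremes:

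- m = 0.1, k = 5: W = 0.5 + 0.9 = 1.4, and 1 ÷ 1.4 = 0.71.
- m = 0.5, k = 20: W = 10 + 0.5 = 10.5, and 1 ÷ 10.5 = 0.10.

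Changes would be distorted too, over the same range:

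- A 20% rise in the resting rate changes W by 0.2(1 − m) ÷ W. This runs from 0.1 ÷ 10.5 = 1.0% to 0.18 ÷ 1.4 = 12.9%, and would print as 20%.
- A 20% rise in the moving rate changes W by 0.2mk ÷ W. This runs from 0.1 ÷ 1.4 = 7.1% to 2 ÷ 10.5 = 19.0%, and would print as 0% in this row.

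**4. The two clerical items in SAP 8.2.**

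- *HRV label.* The eight HRV metrics are four states by two methods. The sleeping, resting and moving pairs have matching labels. The fourth pair is labelled Waking for `hrv_lfhf_wake` and Walking for `hrv_rmssd_wake`. The variable is consistent with its pair; the label is not.
- *Metric count.* Posture 5 + sleep 3 + HRV 8 + pedometry 2 = 18, where the SAP says 17.

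**The case against.** The strongest reply is that this is proofreading. The written definition of Wake Activity Count is clear, the gap at Resting Activity Count is visible, and a careful programmer would query both. The two entries without a source also lack a closing full stop, and one sits at a page break, so some text may have been lost in the copy reviewed. That would explain the missing names. It does not explain the mismatch, because the conflicting definition and variable are printed together in one entry. It remains true that the error arises only if the SAP is followed literally, and that the device dictionary has not been seen.

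The reply is right about several stronger conclusions that a reader might draw:

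- **That drug tremor at rest would be reported as more waking activity.** Protocol 1.5 does list beta2-agonist effects "which include increased heart rate, palpitations, tremors, decreases in potassium and increases in blood glucose". The same sentence says that CST-107 is given to attenuate them, and nothing in either document says that BioStamp counts register tremor. A correctly defined wake count includes resting periods in any case. The documents do not support this inference.
- **That a real change in movement would go unseen.** Moving Activity Count, Percent Moving Time, Step Count Rate and gait cadence have their own definitions and are modelled separately. Only the wake row loses the moving component.
- **That one listed metric has no analysis.** The sentence after the count of 17 models every category listed, so 17 is a miscount.
- **That the wrong HRV data would be analysed.** The wake variable is printed beside the label. Only the label is wrong.

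**Conclusion.** The mapping of Wake Activity Count in SAP 8.1 is wrong as written. Two of the seven activity metrics, Resting Activity Count and Percent Walking Time, have no source at all. Followed literally, the SAP would put resting-only counts in a described and modelled row labelled as wake activity. Under the assumed ranges (moving share 0.1 to 0.5, moving rate 5 to 20 times resting), that row would show about 10% to 71% of the true wake rate. The direction of the error in level holds whenever the moving rate exceeds the resting rate; the size rests entirely on those assumptions.

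The practical weight is modest: one exploratory row, in Australian and New Zealand subjects, with other movement metrics unaffected and no sample-size or power figure involved. It is still worth correcting, because the row would carry a p-value under the wrong name. The HRV label and the count of 17 are clerical.

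**What to change.** Before database lock, check the BioStamp variable map in SAP 8.1 and 8.2 against the device data dictionary, and then:

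1. Assign `activity_resting` to Resting Activity Count.
2. Name the device variable covering moving plus resting periods for Wake Activity Count. If the device gives none, derive it as the time-weighted combination of the moving and resting rates. Percent Moving Time and Percent Resting Time, both defined as shares of waking time, can serve as weights.
3. Name the source variable for Percent Walking Time.
4. In the same revision, relabel `hrv_rmssd_wake` as Waking HRV RMSSD and change the count of 17 to 18.

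The cost is a few lines of SAP text and the matching table shells. Data collection and the form of the model do not change.

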### *Pupillometry*

The PLR test will be conducted for each eye in duplicate prior to first dose on Day 1 (Baseline), and 4 hours post dose on Day 1, Day 7, and Day 14 of each treatment period. Results from the duplicate measurements and across eyes will be averaged (i.e., the four pre-dose measurements on Day 1 [left eye occasions 1 and 2; right eye occasions 1 and 2] will be averaged). Parameters collected include initial pupil diameter (INIT), diameter at end of constriction (END), average constriction velocity (ACV), maximum constriction velocity (MCV), averaged dilated velocity (ADV) and time to reach 75% of initial resting diameter during pupillary dilation (T75).

All pupillometry data will be listed.

### *Dementia Cognitive Fluctuation Scale (DCFS)*

The DCFS is a questionnaire consisting of 17 items that queries confusion, differences in functioning through the day, sleep patterns and problems, varying levels of alertness, and clarity of thought/communication. The DCFS will be administered during screening, on Day 1 (Baseline), and on Day 14 of each treatment period.

Responses for all 17 items and domain scores will be reported in by-subject listings.

## 8.2. Secondary Endpoints and Analyses

The FAS will be used for all secondary endpoint analyses unless stated otherwise. All inferential analyses are exploratory in nature given that this study was not powered based on any statistical assumptions.

### Cohort A and Cohort B

#### *CANTAB*

Cognition function is assessed using the following CANTAB tests:

- Reaction Time (RTI)
- Verbal Recall Memory (VRM) Phase 1
- Adaptive Tracking Task (ATT)
- Paired Associates Learning Task (PAL)
- Stop Signal Task (SST)

Sponsor: CuraSen Therapeutics, Inc.  
Protocol Number: CST103/CST107-CLIN-011  
Version and Date: ██████ v1.0 / 24May2022

- Delayed Verbal Recall

The cognitive assessments measured as part of the CANTAB tests will be administered prior to dosing on Day 1 (Baseline), and 4 hours after dosing on Days 1, 7, and 14 of each treatment period. Summaries will be presented by cohort, disease type, and treatment sequence.

Absolute values of each key measure at each assessment and changes from baseline will be summarized using descriptive statistics on the FAS. There are sixteen key measures based on the Measures Description downloaded from the CANTAB portal and as described by Cambridge Cognition, which are:

- RTI Median Five-Choice Movement Time: The median time taken for a subject to release the response button and select the target stimulus after it flashed yellow on screen, measured in milliseconds. The measurement name for this parameter in the files downloaded from the CANTAB portal is RTIFMDMT.
- RTI Median Five-Choice Reaction Time: The median duration it took for a subject to release the response button after the presentation of a target stimulus, measured in milliseconds. The measurement name for this parameter in the files downloaded from the CANTAB portal is RTIFMDRT.
- PAL First Attempt Memory Score: The number of times a subject chose the correct box on their first attempt when recalling the pattern locations. The measurement name for this parameter in the files downloaded from the CANTAB portal is PALFAMS.
- PAL Number of Patterns Reached: The number of patterns presented to the subject on the last problem they reached. The measurement name for this parameter in the files downloaded from the CANTAB portal is PALNPR.
- PAL Total Errors (Adjusted): The number of times the subject chose the incorrect box for a stimulus on assessment problems (PALTE), plus an adjustment for the estimated number of errors they would have made on any problems, attempts and recalls they did not reach. The measurement name for this parameter in the files downloaded from the CANTAB portal is PALTEA.
- VRM Free Recall Distinct Stimuli – P1.1: The total number of distinct words that are correctly recalled from the presentation phase by the subject during the P1.1 immediate free recall stage. The measurement name for this parameter in the files downloaded from the CANTAB portal is VRMFR11D.
- VRM Free Recall Distinct Stimuli – P1.2: The total number of distinct words that are correctly recalled from the presentation phase by the subject during the P1.2 immediate free recall stage. The measurement name for this parameter in the files downloaded from the CANTAB portal is VRMFR12D.
- VRM Free Recall Distinct Stimuli – P1.3: The total number of distinct words that are correctly recalled from the presentation phase by the subject during the P1.3 immediate free recall stage. The measurement name for this parameter in the files downloaded from the CANTAB portal is VRMFR13D.
- VRM Delayed Free Recall Distinct Stimuli – P2.1: The total number of distinct words that are correctly recalled from the presentation phase by the subject during the P2.1

delayed free recall stage. The measurement name for this parameter in the files downloaded from the CANTAB portal is VRMFR21D.

- VRM Delayed Recognition Total Correct – P2.2: The total number of target words that the subject correctly recognizes, plus the total number of distractor words that the subject correctly rejects in the P2.2 delayed recognition phase. The measurement name for this parameter in the files downloaded from the CANTAB portal is VRMD22TC.
- ATT Euclidean Distance Mean (Phase 2B): The mean Euclidean distance between Target x/y and Finger Touch x/y coordinates, calculated in pixel over the entire 2B assessed phase of the task. This measure is only calculated during the times that either ‘Finger Lift’ and/or ‘Multi-touch’ are not occurring. The measurement name for this parameter in the files downloaded from the CANTAB portal is ATT2BEM.
- ATT Euclidian Distance Standard Deviation (Phase 2B): The standard deviation of the Euclidean distance between Target x/y and Finger Touch x/y coordinates, calculated in pixels over the entire 2B assessed phase of the task. This measure is only calculated during the times that either ‘Finger Lift’ or ‘Multi-touch’ are not occurring. The measurement name for this parameter in the files downloaded from the CANTAB portal is ATT2BESD.
- ATT Difficulty Multiplier Mean (Phase 2B): The mean of the difficulty multiplier calculated over the entire 2B assessed phase of the task. This measure is only calculated during the times that either ‘Finger/Lift’ and/or ‘Multi-touch’ are not occurring. The measurement name for this parameter in the files downloaded from the CANTAB portal is ATT2BDM.
- ATT Difficulty Multiplier Standard Deviation (Phase 2B): The standard deviation of the difficulty multiplier calculated over the entire 2B assessed phase of the task. This measure is only calculated during the times that either ‘Finger Lift’ and/or ‘Multi-touch’ are not occurring. The measurement name for this parameter in the files downloaded from the CANTAB portal is ATT2BDSD.
- SST Stop Signal Reaction Time: The estimate of time where an individual can successfully inhibit their responses 50% of the time. This covert measurement is sampled from the length of time between the go stimulus and the stop stimulus at which the subject is able to successfully inhibit their response on 50% of the trials. We can infer that this is the time before which all actions become ballistic and the subject is no longer able to cancel their action selection. The measurement name for this parameter in the files downloaded from the CANTAB portal is SSTSRT.
- SST Median RT: All Go Trials: The median reaction time taken across all the valid Go trials in the task. The measurement name for this parameter in the files downloaded from the CANTAB Portal is SSTMRTG.

In addition to the descriptive statistic summaries for the above, for each parameter, a mixed effects model approach will be used to evaluate treatment effect. The model will include change from baseline as the dependent variable, baseline as a covariate, treatment sequence, period, timepoint (i.e, Day 1: 4 hrs post-dose, Day 7: 4 hrs post-dose, Day 14: 4 hrs post-dose), disease type, and treatment as fixed effects, and subject as a random effect. The least square means will be summarized, as well as the least square mean difference between treatments, where the

Sponsor: CuraSen Therapeutics, Inc.  
Protocol Number: CST103/CST107-CLIN-011  
Version and Date: [REDACTED] v1.0 / 24May2022

corresponding p-value for this LS mean difference will be provided. All inferential analyses are exploratory in nature given that this study was not powered based on any statistical assumptions.

Line plots detailing individual subject results of the ATT parameters will be produced.

All CANTAB data, which includes 80 total measurements, will be listed on the FAS.

